Secondary outcome measures	
 • Pain • Radiographic results • MRI results • Alteration in treatment regime based on MRI • Number and proportion of fractures with secondary displacement • Any early or late complications
Statistical considerations and estimated enrollment	
Sample size is estimated from previous studies which included less than 30 participants. The investigators of this study suspect that by enrolling 50 participants the age distribution and variation in fracture pattern will be representative of the background population.
 
Baseline characteristics and outcomes recorded at scheduled FU assessments will be presented using simple summary statistics.

Start of enrollment	October 2021 (estimated)
Last patient/last visit	October 2025 (estimated)
Eligibility inclusion criteria	
Inclusion criteria:
 
 • Children age 2-15 years • Diagnosis of acute LHCF (<5 days) with <5 mm of displacement on plain radiographs • Parental informed consent obtained
Eligibility exclusion criteria	
Exclusion criteria:
 
 • Contraindication(s) to performing an MRI • Unable to participate in follow-up • Existing bone pathology • Previous ipsilateral elbow fracture
Principal Coordinating Investigator	
[name] Department of Orthopedic Surgery Copenhagen University Hospital – Herlev and Gentofte Copenhagen, Denmark
 
[contact] [contact] E-Mail [contact]

Study site	
Department of Orthopedic Surgery Copenhagen University Hospital – Herlev and Gentofte Copenhagen, Denmark

Health authority	
The Danish Data Protection Agency The Danish National Committee On Health Research Ethics

Pubmed Medical Subject Heading [MeSH] terms and keywords
	
Child [MeSH] Casts, Surgical [MeSH] Fracture Fixation [MeSH] Humeral Fractures [MeSH]

Imaging review
	
All images collected will be analyzed by independent radiologists during the study

96

97

98 2 Rationale and purpose of the study

99 The treatment of LHCF is most often surgical with open reduction and fixation [1]. The diagnosis of
100 LHCF is complicated by radiographic inability to show the full extent of the injury into the unossified
101 chondral epiphysis and therefore physicians often opt for open surgical treatment. MRI; however, gives
102 a perfect view of these fractures [2–5]. This project investigates the safety and feasibility of non-

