171 Stage 1 and 2 fractures are considered stable and can be treated non-operatively. Stage 3 fractures are
 172 complete and traverse the entire course of the metaphysis, chondroepiphysis and the articular cartilage
 173 leaving the fragment without any attachment. These fractures can be undisplaced but are always
 174 considered unstable. Treatment controversy arises from the inability to distinguishing stage 1 and 2
 175 from stage 3 on plain radiographs.
 176

[figure not shown]

177
 178
 179

Figure 1 - Song classification.

180 Because of the risk of secondary displacement, operative treatment is often conducted with many
 181 surgeons choosing open reduction and fixation in all cases [19,20]. Operative fixation imposes the risk
 182 of minor complications such as superficial infection, ulcers and granulomas but also major complications
 183 such as deep infection, osteomyelitis, malunion, non-union, growth disturbance and osteonecrosis [21].
 184

185 MRI with specific cartilage sequences (figure 2) can clearly show the chondroepiphysis and studies
 186 have shown that MRI is capable of precisely showing the fracture pattern [2,3,5,22]. Using simple
 187 techniques and advances in technology to prepare the child, MRI has been shown to be feasible in
 188 younger children without sedation or anesthesia in whom this was previously thought necessary [23–
 189 30].
 190

191
 192
 193
 194

Figure 2 - MRI showing LHC. Left: Stage 1, confined to metaphysis. Center: Stage 2, fracture line stops in the chondroepiphysis. Right: Stage 3, traverses the joint cartilage.

195

196 5 Primary and secondary objectives

197 5.1 Primary objective

198

199 To describe the functional outcome two years after non-operative treatment of undisplaced and
200 minimally displaced LHCF in children.

201 5.2 Secondary objective(s)

202

- 203 • Describe the feasibility of performing a subacute MRI of the elbow in children with LHCF within 2-7
- 204 days after the injury without sedation or anesthesia
- 205 • Report MRI findings and classify fractures according to Song classification based on MRI
- 206 • Report the number and proportion of fractures that displace secondarily and their treatment
- 207 • Report final treatment; non-operative or operative
- 208 • Describe radiographic results and compare with MRI
- 209 • Report any early or late complications

210 5.3 Hypothesis

211

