456 **Figure 5 - Modified Mayo Elbow Performance Score.**
 457

458

459 **7.2 Secondary outcomes**

460 **7.2.1 MRI results**

- 461 • Proportion of successful MRIs defined as a completed scan with an image quality that is useful for
- 462 analysis by the radiologist.
- 463 • MRI findings.
- 464 • Song classification based on MRI.
- 465 • Scan length (minutes).
- 466 • Any discomforts for the child during the scan.

467 **7.2.2 Radiographic results**

468 Injury radiographs and subsequent radiographs during FU will be read and described by a senior
 469 orthopedic surgeon.

470 **7.2.3 Secondary displacement**

471 Any secondary displacement and amount of radiographic displacement (mm) is recorded.

472 **7.2.4 Pain**

473 To quantify pain in the patient, an age appropriate rating scale is applied:

- 474 • Age <5 years: Face, Legs, Activity, Cry, Consolability Scale (FLACC)
- 475 • Age >4 years: Faces Pain Scale – Revised (FPS-R)
- 476 • Age >8 years: Visual analogue scale

477 **Face, Legs, Activity, Cry, Consolability Scale (FLACC)**

479 To quantify pain behaviors in children who may not be able to verbalize the presence or severity of pain
 480 FLACC [38] provides a simple framework. The child is observed for at least 2-5 minutes. Legs and body
 481 are observed uncovered. Activity is observed and body is assessed for tenseness and tone.

482

Behavior	0	1	2
Face	No particular expression or smile	Occasional grimace or frown, withdrawn, disinterested	Frequent to constant quivering chin, clenched jaw
Legs	Normal position or relaxed	Uneasy, restless, tense	Kicking or legs drawn up
Activity	Lying quietly, normal position, moves easily	Squirming, shifting, back and forth, tense	Arched, rigid or jerking
Cry	No cry (awake or asleep)	Moans or whimpers; occasional complaint	Crying steadily, screams, sobs, frequent complaints
Consolability	Content, relaxed	Reassured by touching, hugging or being talked to, distractible	Difficult to console or comfort

483

484 Assessment of Behavioural Score:

- 485 • 0 = Relaxed and comfortable
- 486 • 1-3 = Mild discomfort
- 487 • 4-6 = Moderate pain
- 488 • 7-10 = Severe discomfort/pain

489

[figure not shown]
490

491

492

493 Faces Pain Scale – Revised (FPS-R)

494 The Faces Pain Scale – Revised (FPS-R) [39] is used to quantify pain in children above four years of
 495 age. It is a self-report measure of pain intensity developed for children. It was adapted from the Faces

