 496 Pain Scale [40] to make it possible to score the sensation of pain on a 0-to-10 metric. The scale shows
 497 a close linear relationship with visual analog pain scales (VAS) across the age range of 4-16 years.
 498

[figure not shown]

499
 500 **Figure 6 - Faces of the FPS-R. The child is instructed to point to the faces that shows how much pain the child is in at**
 501 **that moment. Faces are scored 0, 2, 4, 6, 8 or 10 from left to right.**

502
 503 FPS-R is easy to administer and requires no equipment except for the photocopied faces (figure 6). The
 504 child is asked to point to the face that shows how much pain the child is in at that moment. Faces are
 505 scored 0-10 so 0 equals no pain and 10 equals very much pain.
 506

507 Visual analogue scale

508 A visual analogue scale (VAS) (Figure 7) is used to quantify pain in children age 8 and above. VAS has
 509 been extensively investigated in quantifying pain in older children [41,42]. The child is asked to put a
 510 mark on the line corresponding to the child's pain at that moment. A mark to the far left equals no pain
 511 and a mark to the far right equals worst possible pain. The line is 10 cm long and the child's mark is
 512 measured from left to right in cm with one decimal e.g., 3.4 cm equaling a VAS of 3.4. If the child cannot
 513 cooperate to using VAS, FPS-R is used instead.
 514
 515

516
 517 **Figure 7 - Visual analogue scale (VAS) for quantifying pain in children age 8 and above.**

518
 519
 520
 521
 522

523 8 Statistical planning

524 8.1 Hypotheses

525

526 Minimally displaced LHCF (Song stage 1, 2 and 3) can be treated non-operatively based on MRI
527 findings with good functional outcomes after two years.

528 8.2 Sample size considerations

529

530 Samples size is estimated from previous studies which included less than 30 participants [22,23]. The
531 investigators of this study suspect that by enrolling 50 participants the age distribution and fracture
532 pattern variation will be representative of the background population. By enrolling 50 patients the
533 investigators suspect that any frequent and serious complications will be found.

534 8.3 Statistical analysis

535

536 Baseline characteristics and outcomes recorded at scheduled FU assessments will be presented using
537 simple summary statistics.

538

- 539 • Categorical variables will be summarized using the frequency and percentage for each category.

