574 sedation or GA [23]. Of the 25 children, 17 (68%) had incomplete stable fracture patterns and six (24%)
575 had complete but minimally displaced fractures. In all, 23 (92%) children could be treated non-
576 operatively. Two children had unstable and displaced fractures and underwent surgery.

577
578 If proven safe and feasible, non-operative treatment for undisplaced and minimally displaced LHCF
579 would relieve the child of hospital admission, anesthesia and surgery and reduce parent's need for time
580 off work and reduce overall healthcare costs.

581
582 The investigators suspect a significant decrease in the need for operative management based on the
583 results of this project.

584 11 Risk analysis

585 The risks that occur in this study are associated with the general risks of non-operative treatment for
586 LHCF.

587 11.1 Treatment-related risks

588 Discomforts/risks from casting:

- 589 • Heat injury
- 590 • Pressure sores and skin breakdown
- 591 • Dermatitis
- 592 • Joint stiffness

593 11.2 Study disadvantages

594 Extra visits to the outpatient clinic. We follow all patients with seven visits to the outpatient clinic. This is
595 four more than with standard treatment and might be viewed as a disadvantage.

596 11.3 Study-related risks

597 11.3.1 Secondary displacement

598 During non-operative treatment of fractures, the risk of secondary displacement is well known. The risk
599 of secondary displacement of an initially undisplaced LHCF varies from 4% to more than 40%
600 depending on the initial stability and displacement [12]. As the initial stability in this study is evaluated by
601 MRI the investigators suspect that the risk of secondary displacement will be close to 4%.

602 **11.3.2 Radiation**

603 In comparison with the standard follow up of LHCF there are four additional visits to the out-patient clinic
604 with radiographs of the elbow in AP, ML and IO view. Collectively, the effective dosage is 0.004 mSv -
605 far below 0.1 mSv and is considered insignificant.

606 **11.3.3 Loss of privacy**

607 Patients' private and confidential medical information may get disclosed and confidentiality broken.
608

609 **11.4 Actions to minimize increased risks**

610 General treatment-related risks will be present whether the patient participates in the study or not. Such
611 risks will be managed by use of standards of treatment, i.e. casting by trained physicians and nurses.
612

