652 (e.g. late presentation to the ED) that dictate more emergent treatment requiring consent with less
653 consideration time.

654
655 The parents will signify their willingness to let their child participate in the study by signing and dating a
656 personal copy of the approved ICF. The consent form must also be signed and dated by a member of
657 the research team and it will be retained as part of the study records. The investigator will keep the
658 original ICF in the ISF and provide the patient's parents with a copy.

659 **13 Adverse event reporting**

660 In this clinical investigation no medical devices are used and based on the risk analyses, AEs or serious
661 AEs (SAEs) according to ISO 14155 are not collected.

662 **14 Data management**

663 This project complies with the EU's General Data Protection Regulation (GDPR) according to the
664 Danish law on data protection *Databeskyttelsesloven* and *Databeskyttelsesforordningen*.

665
666 In order to plan and conduct visits we ask that consent is given to access the patient's EHR. We ask
667 permission to retrieve patient-related data and to read entries regarding visits. We ask permission to
668 access radiographs and MRIs. We ask that access the patient's EHR is given until the conclusion of the
669 project. No access to the patient's EHR regarding the study is made before informed consent to
670 participate is given.

671
672 Consent gives the person responsible for the trial and the relevant authorities direct access to obtain
673 information in the patient's medical records for the purpose of carrying out the project as well as for
674 control purposes.

675 **14.1 Data collection, source data, storage and archiving**

676 Data management will be performed by the PI. Data handling and protection are conducted according to
677 the ISO 14155 guidelines and ICH-GCP and applicable regulations.

678
679 The eCRF collects data from each participant. Specifically all data on each patient participating in the
680 study are documented in the eCRF. The eCRF contains data items as specified in this CIP. Modification
681 of the eCRF will be made only if deemed necessary and in accordance with any amendment to the CIP.

682
683 The patient's hospital records are stored securely in the hospital's EHR (Epic Systems Corporation,
684 Verona, Wisconsin, USA).

685 **14.1.1 Electronic CRF**

686 For this study, an eCRF is designed to accommodate the specific features of the study design. Access

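### Section 13 switches off adverse event collection, and the complications outcome is neither defined nor given a recording item, so harms outside the scheduled assessments are captured unsystematically

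*Protocol*

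**What the plan says.** Section 13 of the protocol reads, in two adjoining pieces, "In this clinical investigation no medical devices are used and based on the risk analyses, AEs or serious" and then "AEs (SAEs) according to ISO 14155 are not collected". It gives two reasons: no device is involved, and the risk analysis.

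Other sections rely on harm data:

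- Section 2: "This project investigates the safety and feasibility of non"-operative treatment based on MRI.
- Section 5.2: "Report any early or late complications" is a secondary objective, and the synopsis repeats it as a secondary outcome measure.
- Section 8.2, on why 50 patients are enough: the "investigators suspect that any frequent and serious complications will be found".
- Section 10 looks ahead to the conclusion: "If proven safe and feasible, non-operative treatment for undisplaced and minimally displaced LHCF" would spare the child admission, anesthesia and surgery.
- Section 19 says that safety will be monitored closely together with the sponsor.

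Section 7.2 defines four secondary outcomes: MRI results, radiographic results, secondary displacement and pain. On displacement it is explicit: "Any secondary displacement and amount of radiographic displacement (mm) is recorded". Section 14.1 limits the eCRF to data items specified in the protocol.

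**The concern.** The protocol names complications as an outcome and foresees a statement about safety, but it turns off the usual route for recording harms and puts no other complete route in its place. If section 13 sets aside only device-type reporting, complications must be captured elsewhere, and the protocol does not say where.

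The direction of the error matters. An event with no field, definition or prompt can be missed, whereas an event that did not occur is unlikely to be added. Incomplete capture therefore lowers the complication count and favors the conclusion that the treatment is safe. An SAP cannot repair this, because it cannot analyze what the eCRF never held.

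**Working it through.** The protocol gives no rate, power or precision figure for complications, so there is no figure of its own to reproduce. The check is mainly textual.

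**Step 1: which harms have a scheduled item?** Harms are those named in sections 4.3, 4.4, 11.1 and 11.3.1. Items are those in Table 1 and sections 6.2.6, 6.2.7, 7.1 and 7.2.

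| Harm | Scheduled item | Defined as an event to count? |
|---|---|---|
| Secondary displacement | Radiographs, visits 5 to 10; mm recorded | Yes |
| Nonunion, malunion, growth disturbance | Radiographs, visits 5 to 10 | No |
| Varus or valgus deformity | Carrying angle, visits 6 to 10 | No threshold given |
| Nerve signs | Neurovascular check, visits 5 to 10 | No |
| Joint stiffness | Motion arc in the modified MEPS, visits 6 to 10 | Through the score only |
| Heat injury, pressure sores, dermatitis | Cast condition, visit 5 only | No |
| Complications of later surgery for secondary displacement | None specific | No |
| Other events between visits | Section 6.2.8: documented at the next regular visit | No field specified |

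The cast check falls at day 12 (± 3). Casting usually lasts about four weeks, and the footnote to Table 1 allows two more, so 4 + 2 = 6 weeks. No skin or cast item follows visit 5.

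**Step 2: does the risk analysis support section 13?** Section 11.1 lists the casting harms, and section 11.3.1 cites a displacement risk from 4% to more than 40%. It describes harms to be expected, so it is a weak ground for not collecting them.

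**Step 3: how much could incomplete capture matter?** This is an illustration for a harm without a scheduled item. Inputs are n = 50 (section 8.2), true risk p, and captured share s. The protocol gives neither p for such harms nor s, so both are assumed over a range.

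The chance of recording at least one event is 1 − (1 − p·s)^50. For p = 2% and s = 50%, this is 1 − 0.99^50 = 39.5%.

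| True risk p | s = 100% | s = 75% | s = 50% | s = 25% |
|---|---|---|---|---|
| 1% | 39.5% | 31.4% | 22.2% | 11.8% |
| 2% | 63.6% | 53.0% | 39.5% | 22.2% |
| 5% | 92.3% | 85.2% | 71.8% | 46.7% |
| 10% | 99.5% | 98.0% | 92.3% | 71.8% |

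With no recorded event, the one-sided 95% upper bound on the recorded risk is 1 − 0.05^(1/50) = 5.8%. Dividing by s gives the bound on the true risk: 5.8%, 7.8%, 11.6% and 23.3% for s = 100%, 75%, 50% and 25%.

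The s = 100% column reflects sample size alone. Only the change from left to right belongs to this point.

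**The case against.** The strongest reply is that section 13 is narrow. It sets aside events under the ISO 14155 scheme, partly because no device is studied, and it does not withdraw the complications outcome. The main harm, secondary displacement, is measured in mm and is the only trigger in the stopping rule of section 19.1. Three-view radiographs, neurovascular checks, motion, stability, carrying angle and pain are all scheduled. This stands, and it limits the point.

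A reader might go further in four ways that the protocol does not support:

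- **That any finding of safety would rest on unsystematic data, with nonunion, malunion, deformity or nerve signs noted only by chance.** Sections 6.2.6 and 6.2.7 schedule assessments directed at these. What is missing is a rule that turns findings into counted events.
- **That section 6.2.8 loses events from unscheduled visits.** It is a capture route. Section 14 also seeks access to the health record until the project ends, and section 14.1.1 asks for eCRF entry within 14 days of a documentable event. The weakness is that nothing says what to document as a complication.
- **That ending participation under section 6.3.5 biases the count.** Those children go to surgery after the initial MRI and never receive the non-operative treatment. Children who displace later come under section 6.3.6, which states no termination.
- **That upper limits for zero events in 50 show the size of this defect.** They hold even with perfect capture.

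The reply does not remove the gap. On the narrow reading, complications still have no definition, list or form, and section 14.1 confines the eCRF to specified items.

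**Conclusion.** The point holds in limited form. Section 13 conflicts with sections 2, 5.2, 8.2 and 19 unless it is confined to device-type reporting, and even then the complications outcome lacks a definition and a recording item. The exposed harms are skin and cast injuries beyond one check at visit 5, complications of later surgery for secondary displacement, and events between visits. Nonunion, malunion and growth disturbance are imaged but not defined for counting.

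The primary outcome and the measurement of secondary displacement are not affected. The bias runs towards safe; its size cannot be derived from the protocol. If 75% to 25% of events without a scheduled item were captured, the one-sided bound after no recorded event would rise from 5.8% to between 7.8% and 23.3%. This assumes 50 evaluable children and the stated shares, and it should not be applied to radiographic or goniometric findings. A smaller non-operative group would widen every bound.

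**What to change.** 1. Reword section 13 to say that only ISO 14155 device-type reporting does not apply, and reconcile it with sections 2, 5.2, 7.2, 8.2 and 19.
2. Add complications to section 7.2, with a list drawn from sections 4.3, 4.4 and 11.1, a definition for each event and a cut-off between early and late.
3. Add one eCRF form (type, date, severity, action, outcome), completed at every existing scheduled or unscheduled visit, with an explicit entry for none.
4. Report each complication as n/N with an exact confidence interval. The interval reflects sample size and does not correct for missed events, so steps 2 and 3 are needed as well.
5. For children who leave under section 6.3.5, report their number and reason. Take any later complications only from the health-record access already covered by consent. Following them at visits to 24 months would reverse section 6.3.5 and add visits, and is not proposed.

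The cost is one eCRF form, a little time at each visit and a short amendment. No visit or procedure is added.

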429 Patient and parents are informed of the MRI findings and the following treatment (operative or non-
430 operative) by the PI.

431 **6.3.5 Operative treatment**

432 If the MRI cannot be completed for any reason, the images are insufficient in establishing fracture
433 pattern or if the MRI shows an unstable fracture which is displaced more than 2 mm, we will suggest
434 operative treatment with Kirschner wire fixation. Further participation in this project will be terminated.

435 **6.3.6 Non-operative treatment**

436 Patients with undisplaced and minimally displaced LHCF as seen on MRI will follow a non-operative
 437 treatment protocol (appendix 1). The treatment consists of an above elbow splint until radiographic
 438 union. Radiographic union usually occurs after four weeks; however, treatment will be continued until
 439 callus formation is seen at the cortex of the metaphysis.

440
 441 Fractures that are not complete (e.g., do not traverse both metaphysis, physis, epiphysis and joint
 442 cartilage) are considered stable. Complete fractures displaced <2 mm are considered unstable but still
 443 eligible for non-operative treatment. All patients will be seen for FU as outlined in section 6.2.

444
 445 Any patient with a fracture seen to displace more than 2 mm during FU will be suggested operative
 446 treatment.

447 **7 Definitions of outcome measures and study variables**

448 **7.1 Primary outcome**

449 **7.1.1 Mayo Elbow Performance Score (MEPS)**

450 MEPS consists of four domains; pain, elbow range of motion (ROM), stability and function [35]. We use
 451 a modified MEPS which omits the functional domain because it is not relevant in smaller children. The
 452 total score ranges from 0-100 with higher scores indicating better function (figure 5). If the total score
 453 ranges between 75 and 100, the result is good (satisfactory); 50–74, fair (acceptable); <50, poor
 454 (unsatisfactory) [36]. MEPS has been found to be accurate and reliable compared to other elbow
 455 scoring systems [37].

Criteria	No. of points
PAIN (max., 60 points)	
None	60
Mild to occasional, no medication	40
Moderate to occasional, activity limited, medication	20
Severe to incapacitating	0
MOTION (max. 30 points)	
Arc of extension/flexion:	
>90	30
60–89	20
30–59	10
<30	0
STABILITY (max., 10 points)	
Effect on function of the elbow	
None or mild (does not limit activity)	10
Moderate (impairs certain functions)	5
Severe (markedly limits activity)	0

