687 to the eCRF is password protected. The project's eCRF is stored securely using Research Electronic
688 Data Capture (RedCAP, Vanderbilt University, USA). The eCRF is to be completed in a timely manner
689 after a patient's visit (i.e. 14 days after occurrence of a documentable event).

690 **14.2 Imaging data**

691 Radiographs and MRIs are stored securely in the hospital's Picture archiving and communication
692 system (PACS).

693 **14.3 Confidentiality**

694 Privacy and confidentiality of the patient's medical data will be maintained through the study.

695
696 Fully identifiable information may be reviewed for the purpose of verifying data in the eCRF. This can be
697 carried out by the PI. Personal medical information will be treated as confidential at all times. The
698 informed consent document will contain information about the confidentiality of the medical information
699 and approval for the access.

700 **15 Regulatory affairs**

701 The CIP, associated documents, investigator's financial disclosure, the patient information and ICFs will
702 be sent to a respective EC for evaluation and approval. The relevant EC will be kept informed about the
703 study progress and events according to their specific regulations and procedures.

704 **16 Disclosures and economy**

705 The initiative for this study has been taken solely by the investigators. The investigators and affiliated
706 colleagues have not received any financial payments or other benefits from any commercial entity
707 related to the subject of this project. The investigators declare that they have no conflict of interest.

708
709 Participants do not receive any economic benefits or gifts from the participation in this project.

710
711 All expenses are paid for by the sponsor.

712 **17 Patient insurance**

713 As with any treatment in the Danish healthcare system all patients are insured and covered by The
714 Patient Compensation Association (Patienterstatningen).

715 **18 Study report and publication policy**

716 **18.1 Final Study Report**

717 The results of the statistical evaluation will be summarized in a report, which forms the basis for the
718 comprehensive FSR. The comprehensive FSR forms the basis for all future publications.

719 18.2 Publication

720 The study protocol and the trial will be registered with Clinicaltrials.gov

721

722 The results, both positive, negative and inconclusive, will be sent for submission in a peer reviewed

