723 international orthopedic journal, and the results will be presented at national and international scientific
724 meetings. Reporting will adhere to the STROBE guidelines for cohort studies [31].

725 19 Termination criteria

726 The progress of the study, in particular the enrollment and safety aspects, will be closely monitored
727 together with the sponsor. The sponsor may decide to terminate the. In case of an early study
728 termination, all patients already enrolled in the study will be followed up until the last FU visit as defined
729 in the CIP.

730 19.1 Stopping rules

731 The recruitment will be put on hold for safety reason if:

732

- 733 • Secondary displacement of more than 2 mm during FU in > 75% of cases at interim analysis.

734

735 In such a case, the reported complication will be discussed with the sponsor. The sponsor will decide
736 about the actions to be taken and if the study needs to be stopped or not.

737 20 Deviations from the Clinical Investigation Plan

738 Deviations from the procedures as described in this CIP or altering the CIP without following a defined
739 process are not permitted.

740

741 A CIP deviation is any non-adherence to the protocol that does not involve the inclusion/exclusion
742 criteria, primary efficacy variable, and GCP guidelines. CIP deviations are minor and do not impact the
743 study in a major way. CIP deviations are to be reported to the sponsor within ten working days.

744

745 A CIP violation is any significant divergence from the protocol on the part of the patient, investigator,
746 sponsor, or any other responsible party that affects e.g. the inclusion/exclusion criteria, primary efficacy
747 variable, or GCP guidelines. Violations will be recorded at the study site and in the eCRF.

748 21 Amendments to the Clinical Investigation Plan

749 No changes to the approved CIP are allowed, except when the change removes immediate threats for
750 the patient safety or is of a purely administrative or logistic nature.

751

752 Should there be any need during the performance of the study to change this CIP, an amendment will
753 be developed, issued and approved by or notified to the required bodies.

754

755

756

757 22 Time schedule

Ethics Committee approvals	28.06.2021	to	01.09.2021
First patient/first visit	01.10.2021		
Last patient/first visit	01.10.2023		
Last patient/last visit	01.10.2025		
Data analysis	01.11.2025	to	01.03.2026
Final Study Report	01.03.2026	to	01.06.2026

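### The 75% recruitment-hold trigger in section 19.1 has no stated basis and would almost never fire at ten times the displacement rate the protocol expects

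*Protocol*

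**What the plan says.** Section 19.1 (Stopping rules) puts recruitment on hold for a safety reason on one condition: "Secondary displacement of more than 2 mm during FU in > 75% of cases at interim analysis". The sponsor then discusses the matter and decides whether to stop. The protocol does not give the size or timing of the interim analysis, and 19.1 does not define the cases that form the denominator.

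Section 11.3.1 (Secondary displacement) gives the background figures: the risk "of secondary displacement of an initially undisplaced LHCF varies from 4% to more than 40" per cent. Because stability is judged on MRI in this study, "the investigators suspect that the risk of secondary displacement will be close to 4" per cent.

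Section 6.3.6 (Non-operative treatment) uses the same 2 mm cut for the individual child: "Any patient with a fracture seen to displace more than 2 mm during FU will be suggested operative" treatment. It also says that "Complete fractures displaced <2 mm are considered unstable but still" eligible for non-operative treatment, so the cohort mixes stable and unstable fractures.

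Section 10 (Benefits) cites one earlier MRI series. Of 25 children with a completed scan, 17 had incomplete stable fractures and 6 had complete but minimally displaced ones. These 23 could be treated non-operatively.

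Two other provisions bear on a study-level pause, neither with a number. Section 19 says that progress, "in particular the enrollment and safety aspects, will be closely monitored" together with the sponsor. Section 15 says "The relevant EC will be kept informed about the" study's progress and events.

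**The concern.** A numeric hold rule tells the reader the failure rate at which recruitment pauses for review. Here the event counted is the one at which surgery is suggested to the individual child. The rule waits until more than three in four children have reached that point, while the protocol expects about one in 25. No passage derives 75% from the expected rate, from the cited range or from a rate the sponsor would find unacceptable.

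If the rule is as insensitive as it looks, the only numeric brake on recruiting further children would stay silent even when non-operative treatment fails far more often than planned. Any pause would then depend on unquantified monitoring.

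**Working it through.** The protocol states no probability for this rule, so there is no figure to reproduce.

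**Inputs**
- Trigger: strictly more than 75% (19.1).
- Expected rate 4%; cited range 4% to more than 40% (11.3.1).
- Planned enrolment 50, the largest possible look (6.1.4).
- Cited case mix: 6 complete and 17 incomplete fractures among 23 treated non-operatively (10).

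**Assumptions**
1. The cited displacement rates are comparable with the 2 mm cut in 19.1, which the protocol does not say.
2. Cases means all children treated non-operatively at the look.
3. The look size is not given, so a range is shown.
4. Where 4% is applied to stable fractures alone, that is an assumption; 11.3.1 gives it for the study as a whole.

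**Formula.** At a look on n children the smallest triggering count is k = floor(0.75n) + 1, and the hold probability at true rate p is P(X ≥ k) with X ~ Binomial(n, p).

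**Single looks**

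| n | k | p = 40% | p = 50% | p = 60% |
|---|---|---|---|---|
| 10 | 8 | 1.23% | 5.47% | 16.7% |
| 25 | 19 | 0.03% | 0.73% | 7.4% |
| 50 | 38 | <0.0001% | 0.015% | 1.3% |

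- Over every n from 10 to 50, the maximum is 1.23% at a true 40% and 5.47% at 50%, both at n = 10.
- At n = 25 the expected count is 25 × 0.04 = 1 at the planned rate and 25 × 0.40 = 10 at 40%. A count of 18 (18/25 = 72%) does not trigger.
- Setting P(X ≥ k) = 0.80 and solving for p gives 79.3% (n = 49) to 86.9% (n = 12), and 80.5% at n = 25.

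**Repeated looks** (exact recursion, cumulative chance of a hold)

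| Looks | p = 40% | p = 50% |
|---|---|---|
| 10, 20, 30, 40, 50 | 1.2% | 5.7% |
| Every child, 10 to 50 | 1.6% | 7.7% |
| Every child, 5 to 50 | 9.4% | 21.7% |

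**Looks below 10.** At a true 40% the chance is 8.7% (n = 5), 4.1% (6), 1.9% (7), 0.9% (8) and 2.5% (9). These higher values reflect the noise of very small samples.

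**Cited case mix, every complete fracture displaced**
- Pooled rate: 6/23 = 26.1%. If 4% of the stable fractures also displace: 6/23 + (17/23) × 0.04 = 29.0%.
- Hold chance at n = 25: 2.6 × 10⁻⁷ and 1.6 × 10⁻⁶, both below 0.001%.
- The series is small. The exact (Clopper-Pearson) 95% interval for 6/23 is 10.2% to 48.4%. At the upper limit the pooled rate is 48.4%, or 0.484 + 0.516 × 0.04 = 50.5%. The hold chance at n = 25 is then 0.5% to 0.8%.
- With 6 of 23 complete and all displaced, the stable rate needed to bring the pooled rate to 75% is (0.75 − 6/23)/(17/23) = 66%.

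**The case against.** Five points deserve an answer.

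- **An expected rate and a hold threshold are different quantities, and nothing requires them to be close.** This is true, and the two sections do not contradict each other in the strict sense. The fault is that the threshold has no stated basis and does not respond to rates far above the expected one.
- **The protocol never says that 40% is unacceptable.** Also true. Surgery is described as the usual treatment for this injury, so a high displacement rate might be tolerated. The protocol does not make that argument, and it labels the hold a safety measure. The pattern is similar at 50% and, for all but the smallest looks, at 60%.
- **An analysis plan may define the interim.** It may, and the absence of look size and timing is not the complaint. The 75% is fixed in this protocol, and the result holds for every single look from 10 to 50 and for repeated looks in that range.
- **The case-mix argument is soft.** This has weight. If cases meant unstable fractures only, failure of all of them would trigger the rule, although section 3 speaks of cases included in the study, which favours the wider reading. The series is small, and this cohort admits fractures displaced up to 5 mm on radiographs. The interval around 6/23 covers sampling error only, not that difference in spectrum.
- **Other safeguards exist.** Follow-up radiographs, the control MRI for unstable fractures and suggested surgery beyond 2 mm protect the individual child. The sponsor may also act at its discretion, and section 21 allows changes that remove an immediate threat to safety. These reduce the practical harm, but they do not make the only quantified recruitment trigger work.

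**Conclusion.** The concern holds and should be fixed. For looks at about 10 or more children, the rule has at most a 1.2% chance of pausing recruitment at a single look when the true rate is ten times the expected one (1.6% with a look after every child from 10 to 50). It becomes likely to fire only when the true rate is around 80% or above. Under the one case mix the protocol cites, it would not signal the failure of every complete fracture.

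The conclusion depends on reading cases as all non-operatively treated children, on treating the cited rates as comparable with the 2 mm cut, and on looks of 10 or more. The 40% is an illustration: the cited range is for initially undisplaced fractures, whereas this cohort also admits minimally displaced ones.

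**What to change.** Amend 19.1 so that the trigger is tied to the figures in 11.3.1. The sponsor should reset it as a count-based boundary derived from its expected displacement rate and a rate it chooses as unacceptable, or state why 75% is kept. The paragraph should say which children are counted and name the look or looks (or point to where they are defined). It should also give the hold probability at both rates. Optionally, tabulate displacement at the interim separately for complete and incomplete fractures on MRI, using data already collected. No boundary is proposed here; that choice belongs to the sponsor.

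The cost is one amended paragraph. A lower threshold brings some chance of a temporary hold when the treatment is acceptable, and that chance grows if the true rate is above 4%, so it should be shown over a range of rates. The consequence of a false alarm is limited, because under 19.1 a hold only starts a discussion with the sponsor.
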